4.2.1.5 Sensitivity Analyses of the Primary Endpoint

No sensitivity analysis is planned for the primary estimand.

4.2.1.6 Supplementary Analyses of the Primary Endpoint

The supplementary analysis of the primary endpoint using the primary estimand will be conducted by replacing the direct LDL-C with the LDL-C derived from the Friedewald equation with reflex ultracentrifugation using the analysis model specified in Section 4.2.1.4.

4.2.1.7 Subgroup Analyses

The primary endpoint will also be assessed based on the intensity of the statin background therapy at baseline. Both descriptive and inferential statistics will be presented.

Additionally, the subgroup analysis will be conducted based on Ezetimibe use at baseline (categorized as ‘Yes’ and ‘No’) and direct LDL-C levels at baseline (categorized as <2.6 mmol/L, >=2.6 mmol/L to <=3.9 mmol/L, and >3.9 mmol/L).

The statistical model described in Section 4.2.1.4 will be applied to each subgroup separately.

If the number of participants is too small within a subgroup, the subgroup categories may be redefined prior to unblinding of the study.

4.2.2 Secondary Endpoint: Percent change from baseline of LDL-C at Week 12

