4.2.1.4 Primary Analysis of Primary Endpoint

The summary measure for the primary endpoint will be the difference in least squares mean of percent change from baseline of direct LDL-C at Week 12. The primary endpoint will be analysed using a MMRM on the FAS. Percent change from baseline in direct LDL-C at each post-baseline visit will be used as the dependent variable. The model will include the fixed effects of baseline direct LDL-C, treatment group, visit, and treatment-by-visit interaction, and the random effect (random intercept) of participant. The Restricted Maximum Likelihood estimation approach will be used with a compound symmetry covariance structure for repeated measures.

In case of non-convergence, an ANCOVA model will be run. The model will include the fixed effects of baseline direct LDL-C and treatment group as covariates. In this model, the dependent variable will be the percent change in direct LDL-C from baseline to Week 12.

The results will be summarized by the difference in least squares means, 95% confidence interval, and p-value.

The hierarchical testing strategy will be employed to strongly control the familywise error rate at the 0.05 level (2-sided), as described in Section 3.3.3.

The primary endpoint will also be characterized by descriptive statistics (as defined in Section 3.3.1) at each scheduled visit and visualized with line plot.

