4.2.2.7 Subgroup Analyses

The subgroup analysis described in Section 4.2.1.7 will be conducted for this secondary endpoint as well.

4.2.3 Secondary Endpoint: Percent change from baseline of lipid parameters and inflammatory markers at Week 12 (hypothetical strategy for ICEs defined in the CSP)

The following lipid and inflammatory parameters will be analysed as secondary endpoints using same model as described in Section 4.2.1.4:

- Non-HDL-C
- VLDL-C
- ApoA1
- ApoB
- Total cholesterol
- HDL-C

- Triglycerides
- Lp(a)
- Remnant cholesterol
- hsCRP

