4.2.3.7 Subgroup Analyses

A subgroup analysis may be conducted to assess the impact of baseline lipoprotein(a) [Lp(a)] levels on the treatment effect on Lp(a). The analysis will stratify participant based on their baseline Lp(a) values, as below:

- Lp(a) < 50 mg/dL
- Lp(a) ≥ 50 mg/dL

The primary analysis described in Section [4.2.3.4](#) will be applied separately to each Lp(a) subgroup. If the number of participants is too small within a subgroup, the subgroup categories may be refined prior to unblinding of the study.

4.2.4 Secondary Endpoint: Percent change from baseline of lipid parameters and inflammatory markers at Week 12 (treatment policy strategy for ICEs defined in the CSP)

The lipid and inflammatory endpoints are detailed in Section [4.2.3](#).

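### The subgroup analyses report an effect within each level but no estimate of how the effect differs between levels

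*SAP*

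**What the plan says.** For the primary endpoint, SAP 4.2.1.7 names three subgroup factors. The first is statin intensity at baseline, for which "Both descriptive and inferential statistics will be presented". For the other two, "the subgroup analysis will be conducted based on Ezetimibe use at baseline (categorized as ‘Yes’ and ‘No’) and direct LDL-C levels at baseline", the latter in three bands. The method is the same for all: "The statistical model described in Section 4.2.1.4 will be applied to each subgroup separately".

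The model in SAP 4.2.1.4 is the primary MMRM: "The model will include the fixed effects of baseline direct LDL-C, treatment group, visit, and treatment-by-visit interaction, and the random effect (random intercept) of participant". Its output is fixed there too: "The results will be summarized by the difference in least squares means, 95% confidence interval, and p-value".

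The approach recurs in three places:
- SAP 4.2.2.7, for LDL-C under the treatment-policy estimand: "The subgroup analysis described in Section 4.2.1.7 will be conducted for this secondary endpoint as well".
- SAP 4.2.3.7, for Lp(a) under the hypothetical strategy. This analysis is optional. Its purpose is stated ("to assess the impact of baseline lipoprotein(a) [Lp(a)] levels on the treatment effect on Lp(a"), and the analysis "will be applied separately to each Lp(a) subgroup".
- SAP 4.2.4.7, which carries the Lp(a) analysis over to the treatment-policy strategy.

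The statistical section of the protocol describes no subgroup analysis.

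**The concern.** A subgroup analysis is normally read for whether the effect of a dose varies with a baseline feature. Refitting the model within each level gives one effect per level but no estimate, standard error or interval for the difference between those effects. For Lp(a) the gap is explicit: the SAP asks an effect-modification question and plans no quantity that answers it.

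Without the contrast, readers tend to compare p-values and conclude that a dose works in one level and not in another. Such a pattern can arise when the true effect is identical in both. The study is meant to inform dose choice and later development, so a misread subgroup table could influence design decisions even though no formal claim rests on it.

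**Working it through.** **1. The plan's own figures.** Protocol 9.2 gives 375 randomized, 15% discontinuation, about 320 evaluable and about 64 per arm. Check: 375 × 0.85 = 318.75, and 75 × 0.85 = 63.75. Both agree. The statement of more than 90% power cannot be recomputed, because the difference and SD are redacted. In SD units the standard error of one dose-versus-placebo difference is √(2/64) = 0.1768. Power of 90% at two-sided 0.05 therefore needs a standardized effect d = (1.960 + 1.282) × 0.1768 = 0.573. I use d from 0.573 to 2.0 as an assumed range.

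**2. Is a between-level contrast planned anywhere?** The only interaction in the 4.2.1.4 model is treatment-by-visit. SAP 4.2.1.7, 4.2.2.7, 4.2.3.7 and 4.2.4.7 add no term to it. No section of either document specifies a treatment-by-subgroup term, an interaction test or a difference between levels with a CI. The possible exposure/response modelling in SAP 4.4 does not concern these subgroups.

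**3. What is reported instead.** Statin intensity is taken as two levels. This is an assumption: 4.2.1.7 gives no number, and Protocol Appendix F splits moderate from high only outside Japan. Levels: 2 + 2 + 3 = 7. With four doses, 7 × 4 = 28 p-values for LDL-C under one estimand and 56 under both. The optional Lp(a) analysis adds 2 levels × 4 doses × 2 strategies = 16. None is adjusted (SAP 3.3.3).

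**4. Precision of the missing contrast.** For one dose versus placebo and two levels with n1 and n2 per arm (n1 + n2 = 64), using Week 12 data only and a normal approximation:

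SE = SD × √(2/n1 + 2/n2); half-width = 1.96 × SE.

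**5. Chance of discordant significance when the true effect is the same in both levels.** Power in a level is p = Φ(d/√(2/n) − 1.96). The chance that exactly one level is significant is p1(1 − p2) + p2(1 − p1). Example at d = 0.573, 50:50: p = Φ(0.573/0.25 − 1.96) = 0.630 in each level, so 2 × 0.630 × 0.370 = 0.466.

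| Assumed split | n1 / n2 per arm | SE relative to overall | 95% half-width | Discordant, d = 0.573 | d = 1.0 | d = 1.5 | d = 2.0 |
|---|---|---|---|---|---|---|---|
| 50:50 | 32 / 32 | 2.00 | 0.69 SD | 47% | 4% | <0.1% | about 0% |
| 70:30 | 44.8 / 19.2 | 2.18 | 0.76 SD | 54% | 13% | 0.4% | about 0% |
| 80:20 | 51.2 / 12.8 | 2.50 | 0.87 SD | 63% | 28% | 3% | 0.1% |
| 90:10 | 57.6 / 6.4 | 3.33 | 1.15 SD | 74% | 57% | 24% | 5% |

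For three LDL-C bands of equal size (assumed), n = 64/3 = 21.3 per arm. Two bands then differ with SE = √(2/21.3 + 2/21.3) = 0.433 SD, a half-width of 0.85 SD.

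**The case against.** The strongest reply is that the information is already there. Each level is reported with its own 95% CI, and the levels of a factor contain different participants. For the hypothetical estimand, a reader can therefore subtract two estimates and add their variances, which is what step 4 does. That stands, and it limits the point to a missing printed contrast. By hand it is only approximate for the multiply imputed endpoints, whose imputation models draw on participants from all levels.

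Further points on the same side:
- SAP 4.2.1.7 and 4.2.3.7 allow categories with too few participants to be revised before unblinding. This reduces the problem of small cells but does not supply the contrast.
- If the effect is large, discordant p-values are unlikely, as the right-hand columns show. Protocol 2.3.2 regards an effect like that of approved PCSK9 agents as possible. Lower doses may do less, so the risk is not nil.
- Separate fits do not assume a common covariance across levels. That is a genuine advantage, which a joint model gives up.
- An imprecise interaction invites the opposite error, reading a non-significant result as proof of no difference. This stands and has to be dealt with in the fix.
- Only the optional Lp(a) analysis is framed as a question about effect modification. The LDL-C subgroups state no such hypothesis.

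**Conclusion.** The point holds as a modest, inexpensive improvement. The plan estimates effects within levels and never the difference between them, and for Lp(a) its stated aim has no planned estimator. On an assumed two-level split, the missing contrast would have two to just over three times the standard error of the overall comparison, with a 95% half-width of 0.69 to 1.15 SD. These figures rest on 64 evaluable per arm, Week 12 data alone and assumed splits.

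Four stronger readings are tempting and are not supported:
- That subgroup uncertainty goes unreported. It does not, because every level has a CI.
- That the highest LDL-C band or the ezetimibe users will be a small cell. Neither document gives any prevalence.
- That separate fits make the variance estimates unreliable. The structure is compound symmetry with a random intercept, so few parameters are estimated, across five arms and several visits.
- That error control or the primary conclusion is weakened. The subgroups lie outside the hierarchy in SAP 3.3.3. The p-value within each level is itself inferred from the 4.2.1.4 output and is not named in 4.2.1.7.

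**What to change.** In SAP 4.2.1.7, and by reference in 4.2.2.7, 4.2.3.7 and 4.2.4.7, add the following.

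- For each factor, fit one MMRM to the full FAS: the 4.2.1.4 terms plus subgroup, baseline-by-subgroup, treatment-by-subgroup, visit-by-subgroup and treatment-by-visit-by-subgroup. With the baseline-by-subgroup term, the mean structure matches that of the separate fits, and only the covariance is shared.
- For each dose versus placebo, report the Week 12 effect in each level and the difference between levels with a 95% CI. For the three LDL-C bands, compare each band with a reference band named in advance.
- Label all subgroup p-values nominal, and state that a non-significant interaction is not evidence of equal effects.
- For the treatment-policy endpoints, compute the contrast in each imputed dataset and pool with Rubin's rules. State that the imputation model in SAP Appendix A holds no subgroup variable other than the endpoint's own baseline value, which may pull differences between levels toward zero.

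The cost is SAP wording and programming, including the pooled contrasts. No new data and no change in sample size are needed. The drawbacks are the assumption of one covariance for all levels and a contrast that will be imprecise.

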4.2.2.1 Definition

The clinical question that this estimand aims to answer is the following:

What is the difference in means of percent change in LDL-C from baseline to Week 12 in participants with dyslipidemia treated with AZD0780 vs placebo, regardless of study treatment adherence, changes in background lipid lowering statin therapy, initiation, change or discontinuation in non-prohibited background lipid lowering non-statin therapy and use of allowed and prohibited concomitant medications, where participants cannot die?

The estimand is described by the following attributes:

- Treatment: AZD0780 or placebo.

- **Population:** Male and female participants of non-childbearing potential, 18 to 75 years of age with dyslipidemia, defined by the inclusion and exclusion criteria. Implemented using the FAS.
- **Endpoint:** Percent change in direct LDL-C from baseline at Week 12
- **Population-level summary measure:** Difference in means of percent change in direct LDL-C from baseline to Week 12 between AZD0780 and placebo.
- **Handling of intercurrent event:** The treatment policy strategy will be used for all ICEs except death in this analysis. With this strategy, efficacy assessments are used for treatment effect estimation regardless of the occurrence of ICEs. In case of death, the hypothetical strategy will be applied.

4.2.2.2 Derivations

Direct LDL-C below the LLOQ for which the exact value cannot be determined, will be replaced with the LLOQ divided by the squared root of 2.

The dependent variable is percent change from baseline to Week 12 in LDL-C. Values taken into consideration in the statistical analysis are derived as:

$$\frac{(y_{V_j} - y_{BL})}{y_{BL}} * 100$$

where

- y_{V_j} represents the efficacy measurement at Visit j , and
 - j refers to the visit number up to the last completed visit, which can take any value from the set of $\{3, 4, 5, 6, 7\}$
- y_{BL} is the efficacy measurement at Baseline.

4.2.2.3 Handling of Dropouts and Missing Data

Monotone missing values will be imputed using different methods depending on whether they occurred prior to or after any of the ICEs described in the CSP (i.e., ICE 1, 2, 3, 4(a) described in [Table 3](#)). Details on the imputation algorithm is outlined in [Appendix A](#) [Missing data handling: MI-RD and placebo-washout imputation](#).

4.2.2.4 Primary Analysis of Secondary Endpoint

The secondary endpoint will be analysed using a MMRM based on the FAS, missing data will be imputed prior to fitting the model, as described in Section [4.2.2.3](#)

The analysis model is specified in Section [4.2.1.4](#).

The secondary endpoint will also be characterized by descriptive statistics (as defined in Section 3.3.1) at each scheduled visit and visualized with line plot.

4.2.2.5 Sensitivity Analyses of the Secondary Endpoint

4.2.2.5.1 Sensitivity analysis 1: Analysis with multiple imputation under the MNAR assumption for all monotone missing data

A sensitivity analysis that does not distinguish between the imputation approach in Step 2, Appendix 7.1 Table 12 for monotone missing data occurring prior to or after any of the ICEs described in the CSP will be conducted. In this sensitivity analysis all monotone missing data will be imputed under the MNAR assumption according to MI-RD or – if MI-RD is not feasible – the placebo washout methodology.

4.2.2.5.2 Sensitivity analysis 2: Analysis without explicit missing data imputation

A sensitivity analysis that does not explicitly impute missing data will also be conducted. In this sensitivity analysis, the analysis method will be the same as the main analysis described in 4.2.2.4 except that missing data will not be explicitly imputed prior to model fitting.

4.2.2.6 Supplementary Analyses of the Secondary Endpoint

The supplementary analysis of the secondary endpoint using the primary estimand will be conducted by replacing the direct LDL-C with the LDL-C derived from the Friedewald equation with reflex ultracentrifugation using the analysis model specified in Section 4.2.2.4.

4.2.2.7 Subgroup Analyses

The subgroup analysis described in Section 4.2.1.7 will be conducted for this secondary endpoint as well.

4.2.3 Secondary Endpoint: Percent change from baseline of lipid parameters and inflammatory markers at Week 12 (hypothetical strategy for ICEs defined in the CSP)

The following lipid and inflammatory parameters will be analysed as secondary endpoints using same model as described in Section 4.2.1.4:

- Non-HDL-C
- VLDL-C
- ApoA1
- ApoB
- Total cholesterol
- HDL-C

- Triglycerides
- Lp(a)
- Remnant cholesterol
- hsCRP

4.2.3.1 Definition

The clinical question of interest is:

What is the difference in means of percent change in other lipid parameters and inflammatory markers from baseline to Week 12 in participants with dyslipidemia treated with AZD0780 vs placebo in the hypothetical condition that all participants could adhere to study intervention and non-prohibited background lipid lowering statin and non-statin therapy, prohibited medications affecting lipid parameters were not available, regardless of whether additional treatment is used, and participants cannot die.

The estimands are described by the following attributes:

- Treatment: AZD0780 or placebo.
- Population: Male and female participants of non-childbearing potential, 18 to 75 years of age with dyslipidemia, defined by the inclusion and exclusion criteria. Implemented using the FAS.
- Endpoint: Percent change in other lipid parameters and inflammatory markers from baseline to Week 12.
- Population-level summary measure: Difference in means of percent change in other lipid parameters and inflammatory markers from baseline to Week 12 between AZD0780 and placebo.
- Handling of intercurrent event: The hypothetical strategy will be used for premature and permanent discontinuation of study treatment; change in background lipid lowering statin therapy; initiation, change or discontinuation in non-prohibited background lipid lowering non-statin therapy and intake of prohibited medications affecting lipid parameters. Efficacy assessments obtained after these will not be included in the analysis. Initiation or changes in other concomitant medication will be handled with treatment policy strategy. Deaths will be handled with the hypothetical strategy.

4.2.3.2 Derivations

Percent change from baseline at Week 12 will be derived according to the specifications in Section 4.2.1.2.

4.2.3.3 Handling of Dropouts and Missing Data

Considerations about missing data is detailed in Section 4.2.1.3.

4.2.3.4 Primary Analysis of Secondary Endpoint

The secondary endpoint will be analysed using a MMRM based on the FAS, in alignment with the primary analysis strategy as described in Section [3.3.1.4](#).

The analysis model is specified in Section [4.2.1.4](#). Multiplicity adjustment defined in Section [3.3.3](#) will not be applied to these endpoints.

4.2.3.5 Sensitivity Analyses of the Secondary Endpoint

Not Applicable.

4.2.3.6 Supplementary Analyses of the Secondary Endpoint

Not Applicable.

4.2.3.7 Subgroup Analyses

A subgroup analysis may be conducted to assess the impact of baseline lipoprotein(a) [Lp(a)] levels on the treatment effect on Lp(a). The analysis will stratify participant based on their baseline Lp(a) values, as below:

- Lp(a) < 50 mg/dL
- Lp(a) ≥ 50 mg/dL

The primary analysis described in Section [4.2.3.4](#) will be applied separately to each Lp(a) subgroup. If the number of participants is too small within a subgroup, the subgroup categories may be refined prior to unblinding of the study.

4.2.4 Secondary Endpoint: Percent change from baseline of lipid parameters and inflammatory markers at Week 12 (treatment policy strategy for ICEs defined in the CSP)

The lipid and inflammatory endpoints are detailed in Section [4.2.3](#).

4.2.4.1 Definition

The clinical question of interest is:

What is the difference in means of percent change in other lipid parameters and inflammatory markers from baseline to Week 12 in participants with dyslipidemia treated with AZD0780 vs placebo, regardless of study treatment adherence, changes in background lipid lowering statin therapy, initiation, change or discontinuation in non-prohibited background lipid lowering non-statin therapy and use of allowed and prohibited concomitant medications, where participants cannot die?

The estimands are described by the following attributes:

- Treatment: AZD0780 or placebo.
- Population: Male and female participants of non-childbearing potential, 18 to 75 years of age with dyslipidemia, defined by the inclusion and exclusion criteria. Implemented using the FAS.
- Endpoint: Percent change in other lipid parameters and inflammatory markers from baseline to Week 12.
- Population-level summary measure: Difference in means of percent change in other lipid parameters and inflammatory markers from baseline to Week 12 between AZD0780 and placebo.
- Handling of intercurrent event: The treatment policy strategy will be used for all ICEs other than deaths in this analysis. With this strategy, efficacy assessments are used for treatment effect estimation regardless of the occurrence of ICEs. In case of death, the hypothetical strategy will be applied.

4.2.4.2 Derivations

Percent change from baseline at Week 12 will be derived according to the specifications in Section [4.2.2.2](#).

4.2.4.3 Handling of Dropouts and Missing Data

Please refer to the approach described in Section [4.2.2.3](#).

4.2.4.4 Primary Analysis of Secondary Endpoint

The secondary endpoint will be analysed using a MMRM based on the FAS, in alignment with the secondary analysis strategy as described in Section [3.3.1.4](#).

The analysis model is specified in Section [4.2.1.4](#). Multiplicity adjustment defined in Section [3.3.3](#) will not be applied to these endpoints.

4.2.4.5 Sensitivity Analyses of the Secondary Endpoint

Not Applicable.

4.2.4.6 Supplementary Analyses of the Secondary Endpoint

Not Applicable.

4.2.4.7 Subgroup Analyses

The subgroup analysis described in Section [4.2.3.7](#) will be conducted for this endpoint as well.

4.2.5 Exploratory Endpoint

The analysis of the exploratory objectives, where required, may be presented in a separate exploratory analysis plan.

4.3 Pharmacodynamic Endpoint(s) (if not already covered as endpoint variables)

Not Applicable.

4.4 Pharmacokinetics

Plasma concentration data of AZD0780 will be summarized by treatment group for each sampling timepoint using number of measurements below LLOQ, arithmetic mean and SD, geometric mean and CV, minimum, median and maximum.

The geometric mean of plasma concentrations versus time will be plotted by dose in a line plot both on the linear and on the log-linear scale.

If data permit a population PK (popPK) model may be developed, possibly with the support of PK data from other studies, using nonlinear mixed effects regression analysis in NONMEM. Exposure/response modeling may also be performed to characterize the relationships between AZD0780 exposure and measures of efficacy (eg LDL-C) and safety. PopPK and Exposure/response analysis will use all available data including data corresponding to both on and off treatment (eg missed doses).

All population PK and exposure/response modeling will be described in a separate data analysis plan. Moreover, the results of any such modeling will be provided in a separate population PK and/or exposure/response report (as an appendix to the CSR or as a stand-alone report).

